7.5.2 Reporting of Special Situations

7.5.2.1 Reporting of Pregnancy

If any pregnancy occurs in a female subject in the course of the study, the investigational product should be discontinued immediately and report the pregnancy to the sponsor. Any pregnancy that occurs after the subject first agrees to participate (by signing the ICF) and during the clinical study (including post-treatment follow-up period and 6 months after the last dose) must be reported to the sponsor using the pregnancy report form by the investigational staff no later than 24 hours of when he/she becomes aware of it.

Pregnancy itself is not regarded as an AE. Induced abortion for pregnancy termination is unnecessary unless there's a medical reason. Early pregnancy termination (for example spontaneous abortion due to complication or other medical reasons, or therapeutic induced abortion) must be reported within 24 hours as an SAE. The medical reason during this course should be recorded as the AE term. Spontaneous abortion is always regarded and reported as an SAE. The subject will be appropriately monitored and taken care of until the end of pregnancy. However, subjective induced abortion for pregnancy termination without medical reason does not need to be reported as an SAE of pregnancy termination.

For male subjects, the pregnancy of their female partners must be reported as an SAE. Their partners will be monitored until the end of pregnancy. Refer to Section 4.1.5 for effective contraceptive measures.

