2. OBJECTIVES AND ENDPOINTS

Objectives	Endpoints
Primary objectives	Primary endpoints
To evaluate the efficacy of CS1001 in subjects with R/R ENKTL;	Objective response rate (ORR) assessed by IRRC according to Lugano 2014 classification
Secondary objectives	Secondary endpoints
To evaluate the efficacy of CS1001 in subjects with R/R ENKTL;	ORR assessed by investigators; CRR, PRR, TTR, DoR assessed by IRRC and investigators;
To evaluate the safety of CS1001 in subjects with R/R ENKTL	Severity and frequency of AEs, and frequency of SAEs
To evaluate the PK of CS1001	To determine the peak and trough serum concentration of CS1001
To evaluate the immunogenicity of CS1001	Number and percentage of subjects who develop ADA
Exploratory objectives	Exploratory endpoints
To evaluate the progression-free survival (PFS) and overall survival (OS) of R/R ENKTL subjects	6-months PFS rate, 6-month OS rate
To evaluate genetic aberrations in R/R ENKTL by whole-exome sequencing test of tumor tissues	The association between genetic aberrations and efficacy

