7. REPORTING OF ADVERSE EVENTS

7.1 ADVERSE EVENTS

7.1.1 Definition of an Adverse Event

An AE is any untoward medical occurrence or any worsening of existing medical conditions after the subject signs the informed consent in a study, regardless of its relationship with the investigational treatment. An AE can, therefore, be any unfavorable and unintended sign, symptom, or disease temporally associated with the use of a medication, whether or not related to the medication. An AE can also be a pre- or post-treatment complication resulting from protocol-specified procedure, overdose, drug abuse/misuse, or occupational exposure. Any occurrence with a worsening or changing nature in the study or resulting from participation is also considered as an AE. All AEs should be recorded on the Adverse Events page on the subject's eCRF. All AEs are graded according to CTCAE v4.03.

The following conditions are not considered as AEs:

- Pre-existing or detected disease, condition, or laboratory finding before the screening visit that doesn't get worse during the study;
- Occurrence without any untoward medical event (for example elective operation, hospitalization due to social reason or for personal convenience);
- Any clinically significant medical occurrence or laboratory finding occurs before the subject signing the informed consent and is unrelated to any protocol-defined procedure. This is considered as a preexisting occurrence and should be recorded in the Medical History page on eCRF.

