7.2 SERIOUS ADVERSE EVENTS

7.2.1 Definition of A Serious Adverse Event

According to the definition from ICH (International Council for Harmonisation), SAE is any adverse medical event that meets any of the following criteria:

- Results in death;
- Is life-threatening (Note: life-threatening in the context of an SAE refers to a reaction in which the patient was at risk of death at the time of the reaction; it does not refer to a reaction that hypothetically might have caused death if more severe);
- Requires in subject hospitalization or prolongation of existing hospitalization (except for hospitalization due to medical insurance reimbursement issue or hospitalization without approval by the study doctor);
- Results in persistent or significant disability/incapacity;
- Is a congenital anomaly/birth defect;
- Other medically significant events.

These medically significant events that may not result in death, be life-threatening or require hospitalization may be considered serious when they jeopardize the participant and may require intervention to prevent one of the outcomes listed above. Medical and scientific judgment should be exercised in deciding whether the event should be reported in the light of expedited reporting rules. Examples of medically significant events include allergic bronchospasm requiring intensive treatment in an emergency room or at home, blood dyscrasias or convulsions that do not result in subject hospitalization, or the development of drug dependency or drug abuse. For the avoidance of doubt, infection resulting from drug deterioration is considered as a medically significant event and should be reported according to the expedited reporting rules.

The following hospitalizations that occur during the course of study should not be considered as SAEs:

- Admission into an emergency room, outpatient, or other departments for <24 hours and not hospitalized (unless is considered "medically significant event" or life-threatening event);
- Planned optional operation before ICF signing;
- Protocol-specified admission for medical/surgical treatment or monitoring;
- Admission for physical assessment;
- Admission for a Grade 1 AE, including overnight hospitalization due to nonmedical reasons after investigational product administration;

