7.2.2 Serious Adverse Event Reporting

Any SAE occurring from the time of ICF signing to 90 days after the last dose of investigational product or the start of new anti-cancer therapy, whichever occurs earlier, must be reported to the designated representative of CRO or the sponsor **no later than 24 hours** when it gets learned of, regardless of causality with the investigational product. After the safety follow-up period, only treatment-related SAEs need to be recorded and reported.

Once an SAE occurs, the investigator should:

• Immediately take appropriate treatment measures for the subject and report to the sponsor as described above, and to drug regulatory authorities, health administrative authorities, and the Ethics Committee according to the local requirements.

Complete the SAE module in the EDC system, after which an automated email will be sent to the designated sponsor representative. In case EDC is down, all applicable modules of the sponsor's SAE form will be completed by the investigator/site staff. The investigator must assess the relationship of each SAE to each specific component of study treatment, complete and sign the SAE Report Form, and submit the completed form within 24 hours to the sponsor pharmacovigilance representative. Follow-up information is submitted in a new SAE report form and marked as the follow-up information of a previously reported SAE.

Any SAE that is unresolved at the end of study or subject withdrawal must be followed up until any of the following condition occurs:

- Event resolves; or
- Event stabilizes; or
- Event returns to baseline level (if baseline level available); or
- The event can be attributable to factors related with a medication other than the investigational product or unrelated with the investigator's behavior, or further information is unable to be obtained (when the subject or medical staff refuses to provide more information or when there's evidence showing the subject is lost to follow-up despite every effort made).

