7.5 REPORTING OF SPECIAL SITUATIONS

7.5.1 Definition of a Special Situation

Reporting of special situations includes reporting of a medication error, drug abuse, misuse, overdose, and pregnancy (regardless of its relationship with any AE). Reports of adverse infant reaction post breast milk exposure and Reports of adverse drug effects associated with product complaints or tip-offs due to occupational exposure are also included.

The Pregnancy Report is used to report any pregnancy after maternal or paternal exposure.

Medication error refers to any unintended error in the prescription, dispensing, or administration of medications made by healthcare providers, subjects, or consumers.

Drug abuse is defined as persistent or occasional intended overuse of medication by a subject.

Misuse is defined as intended, improper use of medication that is not in line with the protocol or prescribing information.

Medication overdose is defined as: occasional or intended use/injection of the investigational product in a dose exceeding the prescribed one. Overdose is defined as: the subject has taken (accidentally or intentionally) a dose exceeding the dose prescribed in the protocol by 20%.

A product complaint is a complaint due to potential bias in the manufacturing, packaging, or distribution of medication.

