8.4 SAFETY ANALYSES

The safety analysis will be performed for the SAS population.

Descriptive statistics will be performed to summarize the exposure of the investigational product, which may contain number of cycles, administrations and dose levels, etc.

All adverse events will be described according to MedDRA and graded according to the NCI CTCAE v4.03. All adverse events that occurred during or after investigational product administration will be summarized by NCI CTCAE grade. In addition, serious adverse events, severe adverse events (Grade 3, 4, or 5 events), drug-related AEs, and AEs causing discontinuation or dose modification of the investigational product will each be summarized. Multiple occurrences of the same event will be only counted once for the most severe event. The proportion of subjects with more than one adverse event will be reported.

All deaths that occur during the study or within the defined follow-up period after the last dose/discontinuation of investigational product will be reported.

Specific laboratory tests, vital signs, physical examinations, and 12-lead ECGs and their changes compared with baseline will be summarized. The values at baseline and each time point post-baseline will be presented by crosstabs, when appropriate.

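### Protocol 7.5.2.1 says pregnancy is not an AE yet makes a partner's pregnancy an SAE, and nothing keeps such events out of the serious-event tables

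*Protocol*

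**What the plan says.** Protocol section 7.5.2.1 gives the general rule: "Pregnancy itself is not regarded as an AE". A pregnancy during the study goes to the sponsor on the pregnancy report form within 24 hours. Spontaneous abortion, and termination for medical reasons, are reported as SAEs. The next paragraph gives a different rule for men: "For male subjects, the pregnancy of their female partners must be reported as an SAE". The partner is then followed to the end of the pregnancy.

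Section 7.5.1 describes the route for both sexes: "The Pregnancy Report is used to report any pregnancy after maternal or paternal exposure".

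The definitions are in section 7. Section 7.1.1 reads "An AE is any untoward medical occurrence or any worsening of existing medical conditions after the subject signs the informed consent in a study", and section 7.2.1 reads "SAE is any adverse medical event that meets any of the following criteria". For any SAE, section 7.2.2 tells the investigator: "Complete the SAE module in the EDC system".

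On analysis, the secondary safety endpoint in section 2 is "Severity and frequency of AEs, and frequency of SAEs". Protocol section 8.4 lists the summaries: "In addition, serious adverse events, severe adverse events (Grade 3, 4, or 5 events), drug-related AEs". The SAP (Safety Analyses, Adverse Events) counts subjects with treatment-emergent AEs and tabulates serious TEAEs in the safety analysis set, which is all treated subjects. Neither document says how a partner's pregnancy is handled in these tables.

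**The concern.** The protocol classes pregnancy as not adverse and, in the same subsection, classes one kind of pregnancy as a serious adverse event. The person concerned is not a subject, has not consented and has not been dosed. A site that follows the sentence literally will complete an SAE entry. The documents describe no record for partners, so the likely place is the male subject's own record (an inference). From there nothing written stops the event reaching the serious-TEAE table.

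At stake is the meaning of a named secondary endpoint. An uncomplicated pregnancy could count for a man and not for a woman, although it is not an adverse event in either case. There are two knock-on effects:

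- **Relatedness.** Section 7.2.2 requires a causality assessment for every SAE, and section 7.3.1 counts undetermined causality as related. A partner's pregnancy so classified could also reach the treatment-related table.
- **Collection window.** Section 7.5.2.1 takes pregnancy reports to 6 months after the last dose. Under section 7.2.2, once safety follow-up ends (90 days after the last dose at most), only treatment-related SAEs are recorded. If the pregnancy rule is read to cover partners, a later partner pregnancy falls under two different instructions.

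**Working it through.** The plan states no figure to reproduce, so the check is a comparison of rules followed by one line of arithmetic.

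**Step 1: is a partner's uncomplicated pregnancy an AE?** Section 7.1.1 requires an untoward medical occurrence, timed from the subject's consent. Section 7.5.2.1 says pregnancy is not an AE. The partner is not a subject. By these rules the answer is no.

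**Step 2: can it be an SAE?** Section 7.2.1 requires an adverse event that also meets a seriousness criterion: death, threat to life, hospitalization, disability, congenital anomaly or other medical significance. The pregnancy fails the first condition by Step 1, and an uncomplicated pregnancy is in itself none of the listed outcomes. Yet 7.5.2.1 requires it to be reported as one. This is the contradiction.

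**Step 3: is another route available?** Yes. Section 7.5.1 assigns pregnancies after paternal exposure to the pregnancy report.

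**Step 4: could the event reach the tables?**

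| Stage | Rule | Effect on a partner's pregnancy |
|---|---|---|
| Site reporting | Protocol 7.5.2.1 | Reported as an SAE |
| Data entry | Protocol 7.2.2 | Entered in the SAE module |
| Population | SAP, Analysis Sets | The partner is not in the set; the male subject is |
| Counting | SAP, Adverse Events | Serious TEAEs by subject; a TEAE must be an AE |
| Exclusion | Neither document | None stated |

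The counting rule gives a programmer grounds to drop the event, but no rule says to drop it, and the reporting rule labels it an SAE. The event could be counted; whether it would be is undefined.

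**Step 5: size.** Planned enrolment is about 80 (Protocol section 4). Assume all 80 are treated, and let k be the number of men whose only serious event is a partner's pregnancy. The change in the proportion of subjects with an SAE is k/80.

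- k = 0: 0 points
- k = 1: 1/80 = 1.25 points
- k = 2: 2/80 = 2.5 points

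The documents give no expected number of partner pregnancies, so k = 0 to 2 is purely illustrative. A man who already has another SAE adds 0, as does an event dropped as a non-AE.

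**The case against.** The strongest reply is that the sentence is a reporting instruction under special situations, not an analysis rule. The SAP counts treated subjects, and a TEAE must first be an AE. Read literally, that already excludes an event in a non-subject that the protocol says is not adverse. This stands against a stronger inference that a reader might draw: that partner pregnancies do enter the SAE endpoint and that each adds 1.25 points. The documents do not establish either. It does not settle the matter, because the same protocol calls the event an SAE and no exclusion is written.

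Several other points also stand.

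- A pregnancy form and expedited reporting can coexist, as 7.5.2.1 already provides for spontaneous abortion. Section 7.5.1 therefore shows that another route exists, not that it is the only one.
- The endpoint in section 2 is worded identically for both sexes. What differs is the reporting route, and so possibly the count.
- Inclusion criterion 11 and section 4.5 require effective contraception to 6 months after the last dose, so no partner pregnancy at all is plausible.
- SAE status can trigger onward reporting to authorities and the ethics committee under 7.2.2. A change of route must not lose that where it is required locally.

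Cautious over-reporting for surveillance is defensible, but it gives no reason to leave the tabulation undefined.

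**Conclusion.** The contradiction is certain and lies in current text: 7.5.2.1 conflicts with itself and with 7.1.1 and 7.2.1, and overlaps the route in 7.5.1. The consequence for analysis is possible rather than shown: a partner's pregnancy could be counted under the male subject, and nothing excludes it. The largest effect is 1.25 percentage points per event, which rests on 80 treated subjects and on that man having no other SAE; the actual effect may be zero. The primary ORR endpoint and the efficacy analyses are untouched. The point deserves correction because the rule is wrong as written and the remedy is very cheap, not because the numbers are likely to move far.

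**What to change.** **Protocol.** Reconcile the partner sentence in 7.5.2.1 with 7.1.1, 7.2.1 and 7.5.1, so that one classification and one route apply. Keep 24-hour reporting to the sponsor and follow-up to the end of pregnancy. State where an adverse outcome in a partner is recorded.

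**SAP.** Add one line: pregnancies of male subjects' partners are listed separately and are not counted in subject-level AE or SAE tables, whatever reporting route is kept. This line settles the analysis question even if the expedited reporting rule stays.

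**Data.** Before lock, check whether any partner pregnancy has been entered as an SAE, and handle any that are found under the reconciled rule.

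The cost is one protocol sentence, one SAP line and one data check. If the reporting route changes, there is one small added task: confirm that any onward reporting required locally under 7.2.2 is still met.

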7.5.2.2 Progression of Cancers

The progression of underlying malignancies will not be reported as an AE.

Hospitalization or death merely resulting from the progression of the underlying malignancies will not be reported as an SAE. If the symptom is not exclusively attributable to the underlying malignancy or the symptom is not an expected result of the progression of the investigational disease, the symptom will be reported as an AE.

Some subjects may experience deterioration of clinical symptoms. In this case, the subject's clinical symptom is a typical manifestation of PD but it's not supported by the change in tumor lesion size; or the disease progression is substantial enough that the investigator may consider it unnecessary to perform any further assessments of disease. And as such, clinical progression will be determined based upon the clinical symptom deterioration. Such cases are rare, and the investigator, therefore, should make every effort to record the objective progression of the underlying malignancy.

An AE that cannot be determined as exclusively resulting from the investigational product will be reported as an AE or SAE.

7.5.2.3 Reporting of Other Special Situations

All other special situations must be recorded by the investigator within 24 hours when he/she becomes aware of it. A special situation that constitutes an AE or SAE, will be reported as an AE or SAE. All reports must contain information regarding the involved investigational product, but not for the concomitant medications. Concomitant medications will not be reported unless it results in an AE. Any improper use of prohibited medication should not Confidential 60/104

be reported as 'misuse' but appropriately recorded as protocol deviation. All clinical sequelae related to these special situations should be reported as AEs using the AE report form. If a special situation results in an SAE, it should be reported using the SAE report form. The report will contain information regarding symptoms, signs, clinical intervention, and outcome.

Overdose

If an overdose occurs, symptomatic and supportive care should be given to the subject. If the dose of the investigational product exceeds that specified in the protocol and has an accompanying AE, the AE will be recorded using the Adverse Event Form. Any of the above situations leading to an SAE should be reported as an SAE.

7.6 LIVER FUNCTION TEST FINDINGS

If ALT or AST > 3 x ULN with elevation in total bilirubin (>2 x ULN), it will be considered as a marker of severe liver injury after ruling out Cholelithiasis or other clinical jaundices that may lead to bilirubin. Therefore, any of the following events must be reported as an AE by the investigator:

- During the course of treatment, ALT or AST > 3 x baseline level; or ALT or AST >2 x baseline level and total bilirubin > 2 x ULN (direct bilirubin 35%) in a subject with baseline transaminase elevation;
- ALT or AST > 3 x baseline level with clinical jaundice during the course of treatment.

The most appropriate diagnosis or clinical test finding (if diagnosis unestablished) will be recorded in the eCRF and reported to the sponsor within 24 hours when the investigator gets aware of it, whether it's an SAE or not.

7.7 OTHER SAFETY CONSIDERATIONS

Any significant worsening of interim or final physical examination, ECG, or other safety assessments (no matter it's required by the protocol or not) must be recorded and reported.

8. STATISTICAL CONSIDERATIONS AND ANALYSIS PLANS

8.1 SAMPLE SIZE DETERMINATION

The primary efficacy endpoint is ORR assessed by IRRC according to Criteria for

Response Assessment of Lymphoma: Lugano 2014 Classification.

8.2.1 Analysis Sets

Efficacy analysis set (EAS) consists of all subjects who received at least one dose of investigational product and confirmed by central pathology.

Safety analysis set (SAS) consists of all subjects who received at least one dose of investigational product. The distribution of subjects, their demographics, other baseline characteristics, and the safety analyses will be based upon the SAS.

Pharmacokinetics analysis set (PKAS) consists of subjects who received at least one dose of investigational product and have available plasma drug concentration data.

Anti-drug antibody analysis set (ADAAS) consists of subjects who received at least one dose of investigational product and have available ADA data.

Biomarker analysis set (BAS) consists of subjects who received at least one dose of investigational product and have available biomarker data.

All analysis sets will be determined prior to database lock.

8.2.2 Demographics and Baseline

Patient demographics and baseline characteristics, for example, age, sex, baseline disease characteristics, ECOG PS, and prior anti-cancer treatment, will be summarized for the SAS. Baseline measurement refers to the last measurement obtained before the first dose of investigational product in a subject.

Continuous variables will be summarized using descriptive statistics (mean, median, standard deviation, minimum, and maximum) and categorical variables will be summarized in terms of the number and percentage of patients in each category.

